5.2.2 Expected statistical significance

A p-value < 0.05 is considered statistically significant.

5.2.3 Method for taking into account missing, unused or invalid data

All missing data will be described in terms of numbers and percentages. No imputation will be performed on the primary endpoint.

5.2.4 Managing changes to the initial strategy analysis plan

NA

5.2.5 Choosing the people to include in analyses

All polyps < 20mm characterized by NBI and standard histology of included patients will be analyzed.

6. Vigilance and management of undesirable events

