The colonoscopy procedure for each patient will be no different from a conventional colonoscopy examination with excision of all polyps visualized and anatomopathological analysis, apart from a brief period of NBI analysis for each polyp detected prior to excision, enabling the polyp to be classified according to existing endoscopic classifications (i.e. NICE classification for adenomatous polyps and WASP classification for scalloped polyps).

This joint CHD-CHU project is original in that there are currently no data on the characterization of colonic polyps in NBI by large groups of "non-expert" endoscopists. Indeed, studies carried out to date on this subject, notably in the United States and England, have involved small numbers of NBI expert endoscopists. A recent "pilot" study carried out at Nantes University Hospital showed that NBI is becoming reliable, with a diagnostic accuracy of over 90%, for differentiating adenomatous polyps from typical hyperplastic polyps, but did not assess the contribution of NBI to the characterization of scalloped polyps, a still poorly understood entity. The technological improvement of endoscopes and the publication in 2016 of a classification (WASP) enabling the recognition of sessile scalloped polyps using NBI now necessitate evaluating the contribution of NBI for the recognition of these lesions. A study of this kind in general and university hospitals is essential to determine the feasibility of community implementation, with the ultimate aim of better detecting scalloped colonic lesions, which are often unrecognized but have a clearly demonstrated degenerative potential, and differentiating them from typical adenomatous polyps. The clinical gastroenterology departments of the CHD and CHU are very involved in clinical research, and collaborate on joint care and research projects. Both are equipped with the latest generation of Olympus and Fujifilm (for CHU de Nantes) systems with NBI, and have a significant endoscopic activity, notably in the field of colorectal cancer screening.

1. Justification of the study

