2.1.2 Primary endpoint

Sensitivity of NBI compared with histological analysis (=reference method). Number of polyps characterized as scalloped (CONECCT IS) on reading by NBI compared with the number of polyps characterized as scalloped on standard histology.

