4.2.2 Description of techniques and analyses

Study diagram :

- All endoscopists participating in the study will receive an initial one-hour training course in NBI polyp characterization, delivered by an expert endoscopist in image analysis ([name] [name], graduate of the DIU 'Endoscopie Diagnostique Avancée').
- A verification test (rate of correct answers >95%) will be carried out before each operator is authorized to take part in the study, based on an independent set of images of 30 colonic polyps.
- Each patient corresponding to the pre-inclusion criteria and agreeing to take part in the study is "pre-included". During colonoscopy, the presence of any polyp(s) smaller than 20mm is determined. The right colon, which is the preferred site for adenomatous scalloped polyps, will be examined with particular attention by a second pass under white light. This 2^{ème} pass is routinely performed in standard practice, for example to check fast-moving areas during colonoscopy, and will only increase examination time by around 2-3 minutes. Patients without a polyp smaller than 20 mm are not included in the study.

- Each polyp measuring less than 20mm will be analyzed in white light and NBI, as follows:
- 1) White-light image analysis

2) Switch to NBI mode by simply pressing the 'NBI' button on the endoscope handle (immediate acquisition of the NBI image with photographic recording in LB and NBI). A prediction of the histological type of polyp according to the CONECCT classification is made by the endoscopist and noted in the CRF, together with the degree of certainty (strong or weak).

The study is limited to 4 polyps per patient. Only data from the first 4 polyps removed will therefore be collected.

- All polyps detected and analyzed by NBI are then removed by excision (forceps excision, mucosectomy) according to the usual procedure and analyzed by conventional histology (gold standard).
- If it is impossible to characterize a polyp by NBI (image of poor quality or diagnosis impossible), the examination will be considered a technical failure of NBI, but the polyp will be removed for histological analysis in accordance with current recommendations.
- If the polyp is not recovered for histological analysis, or if interpretation is impossible (coagulation artifacts after standard resection, for example), the examination will be considered a technical failure of standard histology.

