5.2 Statistics

Responsible for statistical analysis: [name] [name]

5.2.1 Description of planned statistical methods, including schedule of planned interim analyses and statistical justification of number of inclusions

Analysis of primary endpoint:

Sensitivity of the NBI technique to pathological findings for the characterization of colonic polyps (conventional adenomatous [CONECCT IIA] versus scalloped [CONECCT IS]) at colonoscopy will be calculated with its 95% confidence interval.

Secondary endpoints :

- The diagnostic performance (specificity, positive predictive value, negative predictive value, RV+, RV-, diagnostic accuracy (corresponding to the rate of correct responses)) of NBI for the characterization of colonic polyps (conventional adenomatous [CONECCT IIA] versus scalloped [CONECCT IS]) compared with standard histology will be estimated with their 95% confidence interval.

- The sensitivity and specificity of white light compared with standard histology results will be estimated with a 95% confidence interval and compared with those obtained by NBI using a McNemar test.

- If numbers permit, sensitivity analyses will be carried out:

- The sensitivity of NBI for the characterization of CONECCT IH and IS polyps versus CONECCT IIA will be estimated according to the certainty of the polyp characterization in NBI: strong or weak. These 2 sensitivities will be compared using a Chi2 test.

- The same analysis will be carried out on the seniority of the endoscopist: junior or senior.

- The same analysis will be performed according to polyp size: 1-5mm vs. 6-9mm vs. 10-20mm or 1-5mm vs. 6-20mm depending on numbers.

Number of subjects required :

Over 48 months, we plan to include 690 patients at Nantes University Hospital and the CHD de Vendée, with the aim of characterizing at least 690 polyps measuring less than 20 mm. About 50% of these will be CONECCT IIA polyps, 40% CONECCT IH and 10% CONECCT

IS. In addition, a majority of these polyps will be <5 mm in size (\approx 60%), \approx 30% between 6-9 mm and \approx 10% >10mm.

Assuming that 5% cannot be analyzed, and that the sensitivity of the NBI is 90%, we can estimate our sensitivity with a confidence interval of \pm 3%.

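### The analysis set in 5.2.5 leaves out polyps that NBI could not read, so the primary sensitivity is conditional on an NBI reading and can only match or exceed the figure over all histologically scalloped polyps

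*Combined protocol and SAP*

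**What the plan says.** - **Analysis set (5.2.5).** The only rule is "All polyps < 20mm characterized by NBI and standard histology of included patients will be analyzed". The word exclude does not appear, but a polyp needs both results to enter.
- **Unreadable NBI (4.2.2).** For an unreadable examination the rule reads: "impossible to characterize a polyp by NBI (image of poor quality or diagnosis impossible), the examination will be considered a technical failure of NBI". Such a polyp is still excised and sent to histology. Histology that is not recovered or cannot be interpreted is a separate category, a technical failure of standard histology.
- **Primary endpoint (2.1.2).** Sensitivity of NBI against histology, with the NBI count of scalloped polyps "compared with the number of polyps characterized as scalloped on standard histology". The section does not mention polyps that NBI could not read.
- **Missing data (5.2.3).** Missing data are to be described as numbers and percentages, and "No imputation will be performed on the primary endpoint".
- **Precision (5.2.1).** The stated interval is ±3%. It assumes 690 polyps, a 5% share that cannot be analyzed and 90% sensitivity. The 5% is not divided between NBI failures and histology failures.
- **Purpose (Introduction).** "A study of this kind in general and university hospitals is essential to determine the feasibility of community implementation". The primary objective in 2.1.1 specifies non-expert endoscopists.

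**The concern.** An NBI technical failure is an observed result of the test under study, and the polyp's true class is normally available from histology. Requiring an NBI characterization removes it from the denominator. What is then estimated is how often NBI is right when it gives an answer.

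For a study meant to inform use by non-experts in general hospitals, the reader also needs to know how often a scalloped polyp is correctly identified when NBI is attempted. A polyp that NBI could not classify was not correctly identified.

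The rule also treats similar difficulty in two ways. A hard scalloped polyp that is called wrongly with weak certainty counts as a miss. The same polyp recorded as impossible to diagnose does not count at all.

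**Working it through.** **Inputs from 5.2.1.** 690 polyps; about 50% CONECCT IIA, 40% IH and 10% IS; 5% not analyzable; sensitivity 90%; 95% confidence interval. The planned mix gives 690 × 0.50 = 345 IH+IS polyps, of which 690 × 0.10 = 69 are IS. Both denominators are carried through because 2.1.1 targets IH and IS together, while 2.1.2 and the primary analysis in 5.2.1 name IS.

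**Assumed input.** f is the NBI failure rate among histologically scalloped polyps. The documents do not give it. The range used is 1% to 5%. The upper end applies if the whole 5% is NBI failure, spread evenly over polyp types.

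**Step 1: the plan's own figure.** Half-width = 1.96 × √(0.90 × 0.10 / n), treating polyps as independent.
- IH+IS: n = 345 × 0.95 = 327.75, half-width 3.25 points. This agrees with the stated ±3% to rounding.
- IS only: n = 69 × 0.95 = 65.55, half-width 7.26 points.
- IS plus IIA: n = 690 × 0.60 × 0.95 = 393.3, half-width 2.96 points. This also rounds to 3, but adenomas do not belong in the denominator of a sensitivity for scalloped polyps.

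IH+IS is therefore the denominator on which ±3% is a fair benchmark.

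**Step 2: direction.** Let C be the correct calls, R the readable scalloped polyps and F the scalloped polyps with an NBI failure. Section 5.2.5 gives C/R. Over all histologically scalloped polyps the figure is C/(R+F). Since F cannot be negative, C/R is never the smaller of the two.

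**Step 3: size.** With C/R = 0.90, the all-polyp sensitivity is 0.90 × (1 − f) and the shift is 0.90 × f. The last column is the half-width of the all-polyp figure on 345 IH+IS polyps.

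| f | All-polyp sensitivity | Shift (points) | Half-width (points) |
|---|---|---|---|
| 1% | 89.1% | 0.9 | 3.3 |
| 2.5% | 87.8% | 2.3 | 3.5 |
| 5% | 85.5% | 4.5 | 3.7 |

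**Step 4: against the planned precision.** The shift equals the IH+IS half-width at f = 0.0325/0.90 = 3.6%. For IS only, the largest shift in the range, 4.5 points, is below 7.3.

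**Step 5: an example in counts.** Suppose 9 of the 345 IH+IS polyps are NBI failures (2.6%) and 302 of the remaining 336 are correctly called.
- Under 5.2.5: 302/336 = 89.9% (Wilson 95% CI 86.2 to 92.7).
- With failures counted as not correct: 302/345 = 87.5% (83.6 to 90.6).

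The difference is 2.3 points.

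**The case against.** The strongest reply is that the plan is a coherent complete-case plan. Section 4.2.2 defines the failures, 5.2.1 allows for a 5% loss, 5.2.3 rules out imputation and 5.2.5 requires both results. Sensitivity given a reading is a legitimate quantity, and which figure is primary is a choice of estimand. The inequality in step 2 follows from counting failures as misses; it does not show that the bias is material. In addition, 5.2.3 has missing data reported as numbers and percentages, so an overall NBI failure count would ordinarily appear.

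Much of this stands. A reader might infer that 2.1.2 and 5.2.5 contradict each other. The documents do not support that: 2.1.2 is silent on unreadable polyps, and 5.2.5 supplies an analysis set that 2.1.2 does not rule out. The point is a consequence of the analysis set that the plan does not address.

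Three parts of the reply do not remove the point.
- A failure count under 5.2.3 leaves the estimate unchanged and is not broken down by histological type.
- The no-imputation rule is no obstacle, because an NBI failure is a recorded outcome and nothing has to be filled in.
- That the shift may lie inside the confidence interval does not make it harmless. The interval describes random error; this shift has one direction and does not shrink as polyps are added.

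**Conclusion.** The point holds as an inexpensive improvement to the plan. As written, the primary sensitivity is conditional on an NBI reading, is not labelled as such, and has no planned companion figure that includes the failures. The direction is certain and the size is unknown. It is 0.9 to 4.5 points for assumed failure rates of 1% to 5%, given 90% sensitivity among readable polyps. That is larger than the planned precision only on the IH+IS denominator and only above a rate of about 3.6%.

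Two stronger conclusions are tempting and are not supported.
- **That the headline figure will be materially inflated.** The 4.5-point shift needs the whole 5% to be NBI failure, whereas 4.2.2 names histology failure as another source. A 9-point shift (0.90 × 34.5/345) would need all 34.5 of the expected losses to be NBI failures on IH+IS polyps. Nothing in the documents indicates that failures concentrate there.
- **That endoscopists will record hard polyps as impossible to diagnose.** The rule allows it, but the documents say nothing about how often it would happen.

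**What to change.** In 5.2.5 and 5.2.1:

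1. Prespecify NBI sensitivity over all eligible polyps under 20 mm (the first four removed per patient) with interpretable histology. Count an NBI technical failure on a histologically scalloped polyp as not correctly characterized. Leave out only histology failures, which have no reference result.
2. Report it beside the 5.2.5 figure, and label the latter *sensitivity given an NBI reading*.
3. State, before analysis, which of the two is primary.
4. Report NBI failures by histological type.
5. State which polyp set the specificity, predictive values, accuracy and McNemar comparison with white light use, so that measures on different sets are not read as one.

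**Cost.** One extra analysis and some wording. No new procedure or specimen is needed, because failed polyps already go to histology. The all-polyp sensitivity will be slightly less favourable if any failures occur. Its interval will be slightly wider, about ±3.5 to ±3.7 points on IH+IS at failure rates of 2.5% to 5%, against ±3.2 for the conditional figure. If the all-polyp figure is made primary, the precision statement in 5.2.1 should be updated to match.

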6.1 Definitions

Vigilance	This is the monitoring of drugs, medical devices and other
	healthcare products. It also involves preventing the risk of undesirable effects resulting from their use, whether these risks are potential or proven,
Adverse events (AE)	Any harmful event occurring in a person undergoing research involving the human body, whether or not the event is related to the research or to the product to which the research relates.
Adverse reactions (AR)	An adverse event occurring in a person undergoing research involving the human body, when this event is related to the research or to the product to which this research relates.
Effects/ Serious adverse events (SAE)	Any adverse effect/event that : * results in death, * is life-threatening, * results in temporary or permanent disability, * requires or prolongs the patient's hospital stay, * causes a congenital or neonatal anomaly, * is medically important (the list of medically important effects/events is defined by the EMA).
Unexpected adverse events	Any undesirable effect whose nature, severity or course is not consistent with the information on the products, procedures and methods used in the research.
New fact	Any new data that could lead to a reassessment of the risk- benefit ratio of the research or the product under investigation, to changes in the use of the product, in the conduct of the research, or in the documents relating to the research, or to the suspension, interruption or modification of the research protocol or similar research. For trials involving the first administration or use of a health product in people with no medical condition: any serious adverse reaction.
Abuse	Intentional, persistent or sporadic excessive use of a drug accompanied by harmful physical or psychological reactions.
Overdose	Administration of a quantity of drug, given at one time or cumulatively, which is above the maximum recommended dose according to the rules of compliance or use of the product. Clinical judgment should always be applied. (actual overdose: due to too large a raw quantity / relative overdose: due to predisposing factors such as renal insufficiency, hypo-albuminemia)
Misuse or off-label use	Situation where the product is intentionally used in a way that does not comply with the product's specifications for use (e.g. route of administration/posology or indication different from that listed in the reference document).

Medication error (ME)	Corresponds to any proven (or potential) omission or unintentional performance of an act during the care process, in the circuit (from manufacture to administration) involving a product, which may be the cause of a risk or undesirable event for the patient. The risk of error or potential error
	concerns situations where the error has not occurred, has been intercepted but could have occurred.

6.2 List of expected adverse events

Associated processes :

- Colonoscopy AEs

- aches and pains
- uneasiness
- bleeding, digestive bleeding
- perforations
- black stools
- fever
- chills
- spleen hematoma
- infectious risks

- Biopsy AEs

- pain,

- uneasiness
- bleeding, hemorrhage
- perforations
- fever
- chills
- infectious risks ;

The histological analysis process can generate EvI and situations that interfere with the result and therefore the quality of the data required for the study:

- failure in the sample transport and storage process,
- faulty sample preparation
- slide reading/interpretation error

AEs from **drugs administered** for colonic preparation and those administered for anesthesia/analgesia during and after the examination. These risks are described in the SPCs of the drugs concerned, administered within the scope of their marketing authorization.

Evl of pathology under study (suspicion - search for colorectal cancer) :

- Signs suggestive of, or aggravated by, bleeding, anemia and/or signs of martial deficiency.

- Abnormalities or changes in intestinal transit
- Modification of a known polyp

AEs concerning any **ancillary treatments**: expected AEs are listed in the RCP for medicinal products used within the scope of the AMM, or in the instructions for use for DM used in accordance with the CE marking indication, and in the therapeutic procedures implemented in accordance with professional recommendations and good practice.

6.3 Adverse events management

6.3.1 Collection of AE

In the context of this minimal-risk, minimal-constraint research study, the protocol does not involve any change in the usual management of patients, so any adverse events or effects observed will be unrelated to the study.

AE related to the intervention, the pathology studied, co-pathologies and their respective treatments do not need to be entered in the vigilance section of the CRF, nor do they need to be notified to the sponsor if a severity criterion is present.

Under the investigator's responsibility, and following the example of care, the notification of complications arising from these examinations comes under regulated systems: AEs linked to drugs and DMs transmitted to pharmacovigilance systems, materialovigilance, complications of procedures and examinations integrated into the establishments' risk management system.

In this study, which aims to evaluate the diagnostic performance of NBI for the characterization of colonic polyps, only complications and AEs of techniques that could have a potential impact on the protocol objective will be collected and reported if a severity criterion exists.

For this purpose, investigators will be asked to provide the sponsor with an anonymized copy of their declaration made in the appropriate regulated declaration system.

The sponsor therefore wishes to receive :

- All new facts arising in the course of the study

- Any unexpected SAEs arising from the protocol procedure (for both types of analysis: white light/NBI and conventional histology)

- Pregnancy reports

6.3.2 Notification of SAE

SAE are notified to the appropriate vigilance circuits (a copy is kept in the patient's clinical file).

For the purposes of this protocol, the complications required to analyze the objective (see paragraph 6.3.1) are collected in the CRF and will be analyzed according to the study schedule (end of study).

When a severity criterion exists, in the context of RIRCM, it is not necessary to send a notification to the sponsor (entry on the CRF is sufficient).

Only "new facts" that may interfere with the research (new information on the technique, etc.), any SUSAR linked to protocol procedures and pregnancy reports must be transmitted to the sponsor as soon as possible after the investigator has become aware of them.

All correspondence between the investigator and the vigilance cell must be copied to the sponsor at the same time.

6.3.3 Notification period to sponsor

The investigator is responsible for collecting and reporting to the appropriate vigilance system the various complications presented by patients.

It is the investigator's responsibility to note and report all AEs, SAEs, special situations or new facts, with the exception of those previously excluded, whether expected or not, occurring during the entire study:

-from the start of the examination (colonoscopy) -and up to histological analysis

6.4 Methods and duration of follow-up care following the occurrence of undesirable events

All events, particularly serious ones, must be monitored until recovery, consolidation or death (closed event).

NB: If a pregnancy occurs during the course of the study, it should be monitored until the child is born or reaches the age of majority.

7. Administrative and regulatory aspects

7.1 Right of access to source data and documents

Each patient's medical data will only be transmitted to the sponsor or any person duly authorized by the latter, and, where applicable, to the authorized health authorities, under conditions guaranteeing confidentiality.

The sponsor and the regulatory authorities may request direct access to medical records for verification of clinical trial procedures and/or data, within the limits authorized by laws and regulations.

